Defined as the indication of a D-dimer testing or a multidetector computed tomography (**CT**) angiogram by the attending physician in the Emergency Department.

Table 2. Exclusion criteria

Exclusion criteria
Unable to provide informed consent
Contraindication to a contrast-enhanced, PE-protocol, multidetector computerized tomography (CT) pulmonary angiogram: allergy to intravenous contrast medium, or renal failure defined as a creatinine clearance < 30 mL/min, based on the Cockcroft-Gault equation
Anticoagulant therapy at the time of hospital admission
Pregnancy, or breast feeding
Life expectancy of less than 3 months
Diagnosis of pneumothorax, or pneumonia (fever [temperature $\geq 38^{\circ}\text{C}$], and purulent sputum, and new infiltrate in chest X-ray)
Diagnosis of lower respiratory tract infection (fever [temperature $\geq 38^{\circ}\text{C}$], increased sputum volume and/or increased sputum purulence).
Indication of invasive mechanical ventilation at the time of hospital admission
Inability to comply with study assessments

Appendix 1. Cockroft-Gault formula

CrCl (male) = ([140-age] × weight in kg)/(serum creatinine × 72)

CrCl (female) = CrCl (male) × 0.85

02	07/11/2015	all	Addition	Inclusion of breastfeeding as an exclusion criterion	[name]
03	10/02/2016	all	Modification	Modification of the end point “Readmission”	[name]
04	21/09/2016	all	Modification	Clarification of the definition “Initial suspicion of PE”	[name]
05	03/09/2018	all	Modification	New sample size calculation	[name]

*Change:

A: Addition

M: Modification

D: Deletion

1. INTRODUCTION

As stated in the summary of the rational in the protocol version 5 dated 3rd September 2018:

Chronic obstructive pulmonary disease (**COPD**) is a leading cause of morbidity and mortality worldwide and represents a huge economic burden for the healthcare system. COPD patients may suffer from exacerbations, defined as acute worsening of respiratory symptoms that results in additional therapy. COPD exacerbations are independent predictors of mortality in COPD and also drive disease progression, with approximately 25% of the lung function decline attributed to exacerbations.

The exact prevalence of PE in unexplained exacerbations of COPD is unclear based on the current data. Over the past decade, several studies have reported the prevalence of venous thromboembolism (**VTE**) in COPD, primarily from hospitalized patients. However, due to the heterogeneities in race, sample size, study design, research setting, and enrollment criteria, there were remarkable differences in reported data among these studies.

In patients with clinical suspicion of PE, there are some data suggesting that some PE diagnoses are less severe, and these patients might not benefit from anticoagulation therapy. For instance, in the PIOPED study, the prevalence of PE was 10% in patients with a nondiagnostic ventilation/perfusion (**V/Q**) scan and a low clinical probability of PE. Nevertheless, such patients have a low-3-month thromboembolic risk provided they have no proximal deep vein thrombosis (**DVT**). This highlights the important point that not all PEs are clinically important, especially if the main site for potential recurrence is free of clots. Particularly for patients with COPD exacerbations, some PE might be clinically unimportant, and the risk of submitting a patient with a clinically insignificant PE to anticoagulant treatment might outweigh the benefit.

Data from randomized controlled trials regarding the clinical effectiveness of an active search for PE in patients who have unexplained exacerbations of COPD are lacking. We hereby propose comparing health outcomes in patients with unexplained exacerbations of COPD who required hospital admission and who will be randomly assigned to an active search for PE with the use of D-dimer and computed tomography (**CT**) pulmonary angiogram, or to usual care.

The objectives of this Statistical Analysis Plan (**SAP**) are:

- To clearly define all variables, end points/outcomes, parameters, thresholds used for the statistical analyses.
- To define strategies employed regarding missing data on end points and possibly on adjustment variables.
- To describe statistical methods performed during the analyses.
- To define the populations of patients used during the analyses.

2. TRIAL DESIGN AND OBJECTIVES

2.1 Type of study

- Typology: comparison of two strategies of care
- Experimental design: investigator-initiated, phase III, prospective, multicenter, randomized (1:1), open-label with blind end-point evaluation (**PROBE**), parallel-group trial
- Planned intervention: active search for pulmonary embolism
- Control: usual care
- NCT (clinicaltrials.gov): NCT02238639

2.2 Sample size and power consideration

Previous studies have shown short-term rates of death, thromboembolic events, or readmission of approximately 40% at day 90 among patients who required hospital admission because of an exacerbation of COPD (1, 2). An estimated 355 participants will be needed in each trial group to detect a clinically important 10% absolute reduction in the primary outcome (i.e., from 40% to 30%) with 80% power at 5% significance level. The 10% reduction was based on consultation with primary and secondary care colleagues (general practitioners and pulmonologists) who considered a 10% reduction to be small but clinically important. Since an interim analysis showed that 3% of patients were lost to follow-up, the Steering Committee anticipated a 5% loss to follow-up. This inflated each study group to 373 patients, giving 746 patients in total.

2.3 Randomization

In a patient with unexplained exacerbations of COPD requiring hospital admission, randomization should occur in the first 24 hours after admission. The trial will use a computer-generated randomization scheme. Randomization will be stratified by center and, within the centers, performed in blocks of 4 and 6 to ensure balanced distribution of the management groups. Randomization will be

performed centrally via the Internet (www.estudioslice.org), and management allocation will be concealed from all investigators.

2.4 Study design

- Population of patients who will benefit the study results: patients with unexplained exacerbations of COPD requiring hospital admission
- Number of centers: 18 centers in Spain
- Study length: inclusion = 48 months; participation = 3 months (Day 90 +/- 7 days).
- Visit schedule: Cf. section 3 protocol version 5 dated 3rd September 2018.

2.5 Objectives and end points

2.5.1 Primary objective

- To demonstrate the clinical benefits of an active strategy for the diagnosis and treatment of PE compared to usual care in patients with unexplained exacerbations of COPD who require hospital admission.

2.5.2 Primary end points

Primary efficacy end point

- Clinical composite endpoint of death from any cause, non-fatal (recurrent) symptomatic VTE, or readmission for COPD exacerbation within 90 days after enrollment.

Primary safety end point

- Major bleeding within 90 days after enrollment.

2.5.3 Secondary objectives

- To assess the prevalence of PE in patients with unexplained exacerbations of COPD who require hospital admission.

- To identify those clinical variables associated with a diagnosis of PE in patients with unexplained exacerbations of COPD who require hospital admission.
- To determine the positive predictive value of D-dimer testing for the diagnosis of PE in patients with unexplained exacerbations of COPD who require hospital admission.

2.5.4 Secondary end points

Secondary efficacy end points

- Death from any cause within 90 days after enrollment.
- Nonfatal (recurrent) symptomatic VTE within 90 days after enrollment.
- Need of readmission for COPD exacerbation within 90 days after enrollment.
- Length of hospital stay.

Secondary safety end points

- Clinically relevant non-major bleeding within 90 days after enrollment.
- Serious adverse events (**SAE**) within 90 days after enrollment.

2.5.5 Ancillary objectives

- To perform a cost-effectiveness analysis comparing both strategies (i.e., active search for PE versus usual care).

2.5.6 Definition of end points

Confirmation of **(recurrent) symptomatic PE** requires symptoms of PE and a new or an extension of a previous intraluminal-filling defect in (sub)segmental or more proximal branches on PE-protocol chest CT pulmonary angiography.

Confirmation of **(recurrent) symptomatic DVT** requires symptoms of DVT and the following criteria: 1) In the absence of previous DVT investigations at baseline, a non-compressible venous segment on ultrasonography; 2) if there

were previous DVT investigations at baseline, abnormal lower limb CCUS where compression had been normal; or, if previously non-compressible, a substantial increase (≥ 4 mm) in diameter of the thrombus during full compression.

Major bleeding is defined according to the guidelines of the International Society of Thrombosis and Haemostasis (3), as acute clinically overt bleeding associated with one or more among the following: a decrease in hemoglobin of 2 g/dL or more, a transfusion of two or more units of packed red blood cells, bleeding that occurs in at least one of the following critical sites (intracranial, intraspinal, intraocular, pericardial, intraarticular, intramuscular with compartment syndrome or retroperitoneal), bleeding that is fatal (defined as a bleeding event that the central independent committee adjudicate as the primary cause of death or contributing directly to death) and bleeding that necessitates surgical intervention.

A bleeding event is classified as a **clinically relevant non-major** bleeding event if it is overt (i.e., is symptomatic or visualized by examination) not meeting the criteria for major bleeding, requires medical attention or is associated with discomfort for the subject such as pain, or impairment of activities of daily life.

Adverse event (AE): any untoward medical occurrence in a patient or clinical investigation participants, which does not necessarily have to have a causal relationship with the study intervention. An AE can therefore be any unfavorable and unintended sign (including an abnormal laboratory finding), symptom or disease temporally associated with the use of the study medication/procedure, whether or not considered related to the study medication.

Adverse reaction (AR): all untoward and unintended responses to a medicinal product related to any dose. The phrase "responses to a medicinal product"

means that a causal relationship between a study medication and an AE is at least a reasonable possibility, i.e., the relationship cannot be ruled out.

All cases judged by either the reporting medically qualified professional or the sponsor as having a reasonable suspected causal relationship to the study medication/procedure qualify as adverse reactions.

Serious adverse event: an event that fulfils one or more of the following criteria:

- Fatal.
- Immediately life-threatening.
- Results in persistent or significant disability/incapacity.
- Requires or prolongs in-patient hospitalization.
- Is a congenital anomaly/birth defect.
- Any other reason representing a significant hazard comparable to the criteria mentioned above.

Serious adverse reaction (SAR): an adverse event (expected or unexpected) that is both serious and, in the opinion of the reporting investigator, believed with reasonable probability to be due to one of the study treatments, based on the information provided.

Suspected unexpected serious adverse reaction (SUSAR): a serious adverse reaction, the nature or severity of which is not consistent with the applicable product information (e.g. Investigator's Brochure for an unapproved investigational product or summary of product characteristics for an approved product).

Length of hospital stay: defined as the interval (in days) from diagnosis of PE at the emergency department to discharge (i.e., date of discharge minus date of diagnosis).

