2.3 Study subjects

Inclusion criteria (Table 1)

Patients are required to fulfill the following inclusion criteria:

1. Confirmation of COPD according to SEPAR-ALT criteria: post-bronchodilator forced expiratory volume in one second (**FEV1**)/forced vital capacity (**FVC**) < 0.7.
2. Hospital admission because COPD exacerbation without initial clinical suspicion of PE in the Emergency Department (according by the Emergency Department physician evaluation).

Exclusion criteria (Table 2)

A patient will be excluded from the study if ANY of the following apply:

1. Contraindication to multidetector CT pulmonary angiography (allergy to intravenous contrast medium, or renal failure defined as a creatinine clearance less than 30 mL/min, according to the Cockroft-Gault formula [**appendix 1**]).
2. Refusal to give informed consent.
3. Pregnancy, or breast feeding.
4. Life expectancy less than 3 months.
5. Anticoagulant therapy at the time of hospital admission.
6. Diagnosis of pneumothorax, or pneumonia (fever [temperature >38°C two times at least 12 hours apart], and purulent sputum, and new infiltrate in chest X-ray) at the time of hospital admission.
7. Diagnosis of lower respiratory tract infection (fever [temperature >38°C two times at least 12 hours apart], or increased sputum volume and increased sputum purulence) at the time of hospital admission.
8. Indication of invasive mechanical ventilation at the time of hospital admission.
9. Participation in any other investigational drug or device study in the past four weeks.
10. Geographic inaccessibility that precludes follow-up.

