2.5 Study procedures

All patients will receive standard clinical management (usual care) for their COPD exacerbation according to the clinician's preference and local standards.

Intervention group

Patients in the intervention group will have blood samples collected from an antecubital vein, and will undergo D-dimer testing within 12 hours after randomization. Cut-off levels for defining elevated D-dimer will be defined by the Department of Clinical Chemistry at each participating site. For patients with a negative D-dimer, a diagnosis of PE will be ruled out. For patients with a positive D-dimer, a contrast-enhanced, PE-protocol, multidetector CT will be performed. CT pulmonary angiography results will be categorized as positive for PE if an intraluminal filling defect is seen in (sub)segmental or more proximal branches, and will be considered negative if no filling defect is observed. Scans will be considered technically inadequate only if main or lobar pulmonary vessels are not visualized. Though not mandatory, the protocol suggests the use of complete lower limb compression ultrasonography (**CCUS**) to detect concomitant DVT for patients with isolated subsegmental PE.

If the diagnosis of PE is confirmed, patients will receive anticoagulant treatment according to guideline recommendations: parenteral anticoagulation (i.e.,

unfractionated heparin, low-molecular-weight heparin, or fondaparinux) overlapped and followed by vitamin K antagonists; or parenteral anticoagulation followed by dabigatran or edoxaban; or monotherapy with apixaban or rivaroxaban (19).

Control group

Patients in the control group will receive standard clinical management (usual care) for their COPD exacerbation according to the clinician's preference and local standards.

After hospital discharge, all patients (in the intervention and control arms) will be treated according to the national and international recommendations for the management of stable COPD (1, 2).

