3.3 Enrollment and in-hospital period

Start of period: When a given patient is randomized.

End of period: When a given patient is discharged.

Setting: Hospital.

e-CRF entries:

- Randomization group: intervention or control group
- D-dimer test results (Intervention group)
- CT pulmonary angiogram result (Intervention group)
- Symptomatic new or recurrent VTE
- Death
- Primary cause of death
- Major bleeding

- Clinically relevant non-major bleeding
- Serious adverse events
- Treatment for COPD exacerbation
- Hospital discharge

At day 7, it will be recorded if the patient was discharged or not. Hospital discharge is defined as end of hospitalization or if the patient is transferred for long-term rehabilitation.

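### The SAP starts length of hospital stay at a PE diagnosis in the emergency department, a date most randomized patients will not have

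*SAP*

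**What the plan says.** SAP 2.5.4 lists "Length of hospital stay" among the secondary efficacy end points, without limiting it to patients with PE. SAP 2.5.6 gives the only definition in either document: "defined as the interval (in days) from diagnosis of PE at the emergency department to discharge". It then restates the arithmetic as "date of discharge minus date of diagnosis".

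SAP 3.5.2 analyses secondary end points in the evaluable patients of the randomized population under intention to treat, and presents means as an intervention-minus-control difference with a 95% confidence interval. The protocol's study plan schedules length of stay for all patients, whereas it marks D-dimer and CT as intervention group only.

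**The concern.** The start date depends on an event that the design makes uncommon at baseline and looks for in only one arm. Protocol 2.3 requires "Hospital admission because COPD exacerbation without initial clinical suspicion of PE in the Emergency Department". The definition under protocol Table 1 makes an emergency-department order for either test count as suspicion: "Defined as the indication of a D-dimer testing or a multidetector computed tomography". The protocol's own search comes later, since under protocol 2.5 intervention patients "will undergo D-dimer testing within 12 hours after randomization". Controls have no protocol search at all.

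If the sentence is applied as written, the mean difference can be formed only in patients diagnosed with PE. That subset is selected after randomization by the strategy under test, so the result would compare PE found by active search with whatever PE usual care happens to find. It would not compare the randomized groups that SAP 3.5.2 names. SAP 3.6 extends secondary end points to every subgroup, so the problem recurs there.

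**Working it through.** **Step 1. Who has a start date?**

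| Patient | PE diagnosis date under the plan |
|---|---|
| Intervention, negative D-dimer | None: protocol 2.5 treats PE as ruled out |
| Intervention, positive D-dimer, negative CT | None |
| Intervention, positive CT | Yes, but after randomization and not necessarily in the emergency department |
| Control, no PE found by usual care | None |
| Control, PE found by usual care | Yes; the documents give no rate |

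**Step 2. Denominator.** The plan states no figure for length of stay, so its sample size serves only as the denominator. For 40% versus 30%, two-sided 5%, 80% power:

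n = [1.960 × √(2 × 0.35 × 0.65) + 0.842 × √(0.40 × 0.60 + 0.30 × 0.70)]² / 0.10² = 355.9, or 356 per arm (stated: 355).

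355 × 1.05 = 372.75, which gives the stated 373 per arm and 746 in total. Dividing by 0.95 instead gives 374. The difference is immaterial here.

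**Step 3. Patients without a value.** Inputs are the prevalences in protocol 1.1: 3.3%, 16% and 25%. The search is assumed to find every PE in the intervention arm, and any PE diagnosis date is accepted wherever it was made. Both assumptions favour the SAP wording.

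- Intervention patients without a date = 373 × (1 − p)
- All patients without a date, if usual care finds no PE = 746 − 373 × p
- All patients without a date, if usual care finds every PE = 746 × (1 − p)

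| p | Intervention patients with a date | Intervention patients without | All without, no control PE found | All without, every control PE found |
|---|---|---|---|---|
| 3.3% | 12.3 | 360.7 (96.7%) | 733.7 (98.4%) | 721.4 (96.7%) |
| 16% | 59.7 | 313.3 (84.0%) | 686.3 (92.0%) | 626.6 (84.0%) |
| 25% | 93.25 | 279.75 (75.0%) | 652.75 (87.5%) | 559.5 (75.0%) |

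The last two columns bound the answer. If usual care is assumed to diagnose PE in 2% of controls, 373 × 0.02 = 7.5 controls have a date. The total with a date is then 19.8 of 746 (2.7%) at 3.3% prevalence and 100.7 of 746 (13.5%) at 25%.

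**Step 4. The literal reading.** If the diagnosis must be made in the emergency department, fewer patients have a value. Some could still qualify, because protocol 3.2 places screening there until 24 hours after the decision to admit. The documents do not give the share.

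**Step 5. Is there another start date?** None is labelled as length of stay. Protocol 3.3 does bound the in-hospital period without reference to PE: "Start of period: When a given patient is randomized" and "End of period: When a given patient is discharged". The SAP sentence does not use it.

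**The case against.** The best reply is that this is a slip of wording. The study plan shows the end point was meant for everyone, its footnote b refers to the length of the hospital admission, and protocol 3.3 defines discharge without mentioning PE. A literal analysis would leave the control arm almost empty, which would be noticed at once. The counts above therefore measure the wording and do not estimate a likely bias. The SAP also says secondary results should not be used to infer intervention effects. All of this is fair, and it limits the weight of the point. It does not settle which date replaces the stated one. Randomization may follow admission by up to 24 hours, so an unwritten choice between them would be made with data in hand in an open-label trial.

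Two other rescues fail. Restricting the analysis to evaluable patients makes evaluability depend on a diagnosis the intervention is designed to produce. The worst-case or multiple-imputation analyses in SAP 3.2 and 3.5.3 address values that exist but were not observed, whereas here the value is undefined.

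Two practical objections stand in part. The protocol's discharge definition does not say clearly whether a death in hospital ends the stay. The e-CRF is also not available for review, so a recorded discharge date cannot be taken for granted.

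**Conclusion.** The concern holds. As defined in SAP 2.5.6, length of stay has no value for most patients in either arm: about 75% to 98% of the 746, depending on PE prevalence and on how much PE usual care finds. That range rests on prevalences from other populations, and this trial also excludes patients suspected of PE in the emergency department. The conclusion does not depend on the exact figure, because a definition that requires a PE diagnosis cannot support a comparison of the randomized groups.

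The damage is confined mainly to one secondary end point. The primary efficacy analysis, the primary safety analysis and the sample size are untouched. One conditional side effect deserves a check: SAP section 7 removes patients with missing secondary end points from the per-protocol set. If undefined stays were coded as missing, that rule would empty most of the set used for the sensitivity analysis of the primary end point. This should be fixed, and it is easy to fix.

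**What to change.** Before database lock, replace the sentence in SAP 2.5.6 with: *Length of hospital stay = date of index hospital discharge (as defined in protocol 3.3) minus date of randomization, for every randomized patient in both arms.*

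Randomization is suggested because protocol 3.3 already starts the in-hospital period there and protocol 2.8 times the visits from it. Date of admission, which is closer to footnote b of the study plan, is also acceptable if used identically in both arms. What matters is one common start date, written down in advance. Keep the planned difference in means, report the number of in-hospital deaths per arm beside it, and add a clause saying whether a death in hospital counts as the end of the stay.

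The cost is this one definition in the SAP. SAP 3.5.2 stays as it is and no patient procedure changes. SAP section 7 already treats late randomization relative to admission as a deviation, which presupposes that both times are known, and hospital discharge is a listed e-CRF entry. The sponsor should confirm that this entry holds a date and is not only a yes/no item.
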